### 6.2. Timing of Analyses

The final analysis will be performed after database lock.

### 6.3. Analysis Populations

The composition of analysis populations, including reasons for participant exclusion will be presented by treatment group and overall ([Table 9](#)). A listing of all participants and visits excluded from the analysis populations will be provided ([Listing 5](#)).

#### 6.3.1. Safety Population

The Safety Population includes all participants who received at least one dose of study vaccination. Participants will be analyzed according to actual study product received.

#### 6.3.2. Full Immunogenicity Population

The Full Immunogenicity Population consists of all participants who received any study product and contributed both pre- and at least one post-study vaccination blood samples for immunogenicity testing for which valid results were reported. Participants will be analyzed according to actual study product received.

#### 6.3.3. Per Protocol Immunogenicity Population

The Per Protocol (PP) Immunogenicity Population includes all participants in the Full Immunogenicity Population with the following exclusions:

- Data from all available visits for participants found to be ineligible at baseline.
- Data from all visits after major protocol deviations, such as:
  - Receipt of an incorrect study vaccination.
  - Second or third vaccination not received.
  - Second or third vaccination received out of window.
  - Receipt of any of the following:

- Licensed, live vaccine within 30 days of any vaccination.
- Licensed, inactivated vaccine within 14 days of any vaccination.
- Investigational products at any time during study period.
- Data from any visit that occurs out of window.

All protocol deviations will undergo a review prior to database lock, blinded to outcome value to determine if the affected visit and any subsequent visits will be excluded from the PP Immunogenicity Population for the affected participant(s).

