6. Participation in a previous *Campylobacter* study or reports having received vaccination against *Campylobacter* within the last 3 years.
7. History of microbiologically confirmed *Campylobacter* infection in the last 3 years.
8. Occupation involving handling of *Campylobacter* bacteria or vaccine products currently or in the past 3 years.
9. Use of immunosuppressive/immunomodulating disease therapy within 90 days
10. Received Ig or other blood products (with exception of Rho D Ig) within 90 days prior to enrollment.
11. Have a history of severe reactions following previous immunization with any licensed or unlicensed vaccine.
12. Known hypersensitivity to any components of vaccine, adjuvant, or diluent.
13. Received or plan to receive a licensed live vaccine within 30 days prior to 1st vaccination and to 30 days after the last vaccination.
14. Received or plan to receive a licensed, inactivated, vaccine within 14 days prior to 1st vaccination to 14 days after the last vaccination, or a seasonal influenza and/or COVID-19 vaccine \pm 7 days from study product vaccination.
15. Individuals in whom the ability to observe possible local reactions at the eligible injection sites (deltoid region) is unacceptably obscured due to a physical condition or permanent body art.
16. Within 14 days prior to vaccination has received an oral or parenteral (including intra-articular) corticosteroid of any dose for 5 or more days, or high-dose inhaled corticosteroids.
 - a. High dose defined per age as using inhaled high dose per reference chart (https://www.nhlbi.nih.gov/files/docs/guidelines/asthma_qrg.pdf)
17. Current or history of alcohol or drug abuse within one year prior to enrollment.

18. Have any diagnosis, current or past, of schizophrenia, bipolar disease, or other psychiatric diagnosis that may interfere with subject compliance or safety evaluations.
19. Have been hospitalized for psychiatric illness, history of suicide attempt, or confinement for danger to self or others within one year prior to enrollment.
20. Are pregnant, breastfeeding, or plan to become pregnant or breastfeed at any given time during the study.
21. Have an acute illness as determined by study clinician licensed to make medical diagnoses and listed on the Form FDA 1572 as the site PI or sub-investigator, within 72 hours prior to enrollment.

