 - a. An acute illness which is nearly resolved with only minor residual symptoms remaining is allowable if, in the opinion of a study clinician licensed to make medical diagnoses and listed on the Form FDA 1572 as the site PI or sub-investigator, the residual symptoms will not interfere with the ability to assess safety parameters as required by the protocol.
22. Received an investigational product within 30 days prior to the first study vaccination or expect to receive an investigational product during the study period.
 - a. Including vaccine, drug, biologic, device, blood product, or medication, other than from participation in this trial.
23. Have abnormal screening laboratory values within 30 days prior to enrollment.
 - a. Refer to [Appendix B](#) for range of normal laboratory values.
 - b. Screening laboratory values that are outside acceptable range but are thought to be due to an acute condition or due to laboratory error may be repeated once. [see MOP]

4.1.3 Subject Qualification Criteria for Vaccinations 2, 3

If Halting Criteria in [section 7.6](#) are met, further study vaccinations will be halted pending SRC and Safety Monitoring Committee (SMC) review.

Any subject with 1) a SAE assessed as related to the vaccine, or 2) a PIMMC regardless of vaccine relatedness criterion excluding subjects with a history of PIMMC, will be discontinued from study vaccinations.

Subsequent vaccinations may proceed if the following criteria are all answered yes:

1. Oral temperature less than 100.4°F.
2. Negative urine pregnancy test, as applicable.
3. Females of childbearing potential continue to agree to use acceptable contraception for the duration of the trial (including the safety communication follow up period).

4. Has not received or plans to receive a licensed, inactivated, vaccine within 14 days prior to 1st vaccination to 14 days after the last vaccination or a seasonal influenza and/or COVID-19 vaccine \pm 7 days from study product vaccination.
5. Has not received or plans to receive a licensed live vaccine through 30 days after the last vaccination.
6. Within 14 days prior to vaccination has not received an oral or parenteral (including intra-articular) corticosteroids of any dose for 5 or more days, or high-dose inhaled corticosteroids.
 - a. High dose defined per age as using inhaled high dose per reference chart (https://www.nhlbi.nih.gov/files/docs/guidelines/asthma_qrg.pdf)

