5.5 Protocol Deviations

A protocol deviation is any noncompliance with the clinical trial protocol, GCP, or protocol-specific MOP requirements. The noncompliance may be either on the part of the subject, the site PI, or the site personnel. As a result of deviations, corrective actions are to be developed by the site and implemented promptly.

These practices are consistent with ICH E6:

- 4.5 Compliance with Protocol, Sections 4.5.1, 4.5.2, and 4.5.3
- 5.1 Quality Assurance and Quality Control, Section 5.1.1
- 5.20 Noncompliance, Sections 5.20.1, and 5.20.2.

It is the responsibility of the site PI and personnel to use continuous vigilance to identify and report deviations within five working days of identification of the protocol deviation, or within five working days of the scheduled protocol-required activity. All deviations must be promptly reported to DMID per the Statistical and Data Coordinating Center (SDCC) protocol deviation reporting procedures.

All protocol deviations, as defined above, must be addressed in study subject eCRFs. A completed copy of the DMID Protocol Deviation Form must be maintained in the Regulatory File, as well as in the subject's chart. Protocol deviations must be sent to the local IRB/IEC per their guidelines. The site PI and personnel are responsible for knowing and adhering to their IRB requirements.

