9.4.1 Analysis Populations

The Safety Population includes all subjects who received at least one dose of study vaccination.

The Modified Intent-to-Treat (mITT) Population consists of all subjects who received any study product and contributed both pre- and at least one post-study vaccination blood sample for immunogenicity testing for which valid results were reported.

The Per Protocol (PP) Population includes all subjects in the mITT Population with the following exclusions:

- Data from all available visits for subjects found to be ineligible at baseline.
- Data from all visits after major protocol deviations, such as:
 - Receipt of an incorrect study vaccination
 - Second or third vaccination not received
 - Second or third vaccination received out of window
- Receipt of any of the following:
 - Licensed, live vaccine within 30 days of any vaccination
 - Licensed, inactivated vaccine within 14 days of any vaccination
 - Investigational products at any time during study period

- Data from any visit that occurs substantially out of window

In the case of mis-randomization, subjects will be analyzed according to the study product actually received for all analysis populations.

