### 7.2. Protocol Deviations

All protocol deviations will be classified as major or minor using the definitions below.

- Major Deviation – A deviation from the Institutional Review Board-approved protocol documents that have, or may have the potential to, negatively impact the rights, welfare, or safety of the participant, or to substantially negatively impact the scientific integrity or validity of the study.
- Minor Deviation – A deviation that does not have the potential to negatively impact the rights, safety, or welfare of participants or others, or the scientific integrity or validity of the study.

Prior to database lock, the SDCC will provide a listing of all protocol deviations with an initial classification of major or minor to DMID who will review and make final determinations to be included in the database lock.

A summary of participant-specific protocol deviations will be presented by deviation category, deviation type, and treatment group for all participants ([Table 4](#)). All participant-specific protocol deviations and non-participant-specific protocol deviations will be presented in data listings ([Listing 3](#) and [Listing 4](#), respectively).

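### Could an influenza or COVID-19 vaccine that eligibility permits 8–14 days from a dose still remove a participant's visits from the per-protocol set?

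*SAP*

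**What the plan says.** **Eligibility.** Exclusion 14 in Protocol 4.1.2 bars a licensed "inactivated, vaccine within 14 days prior to 1st vaccination to 14 days after the last vaccination, or a seasonal influenza and/or COVID-19 vaccine" within ±7 days of a study dose. Criterion 4 for doses 2 and 3 in Protocol 4.1.3 repeats both parts: "vaccine within 14 days prior to 1st vaccination to 14 days after the last vaccination or a seasonal influenza and/or COVID-19 vaccine", again at ±7 days. The parts are joined by *or*. Neither criterion says *except*, and neither says whether a COVID-19 vaccine counts as inactivated.

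**Per-protocol set.** Protocol 9.4.1 and SAP 6.3.3 carry over only the 14-day line, "Licensed, inactivated vaccine within 14 days of any vaccination", and mention neither influenza, COVID-19 nor 7 days. In the SAP the line stands under "Data from all visits after major protocol deviations, such as", so it is an example within a class. The section ends with a safeguard: "All protocol deviations will undergo a review prior to database lock, blinded to outcome value", to settle whether the affected visit and later ones are dropped.

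**Deviations.** Protocol 5.5 reads "A protocol deviation is any noncompliance with the clinical trial protocol, GCP, or protocol-specific MOP requirements". Under SAP 7.2 the coordinating center sends a "listing of all protocol deviations with an initial classification of major or minor to DMID who will review and make final determinations" before the database is locked.

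**Visit windows.** Protocol 9.4.1 drops "Data from any visit that occurs substantially out of window". SAP 6.3.3 has the same rule without the adverb, and SAP 15 does not list the difference.

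**The concern.** Every ±7-day window lies inside the 14-day span. For an inactivated influenza vaccine the second clause therefore adds nothing unless it relaxes the first, which suggests that an exception was meant. A shot 8–14 days from a dose would then be allowed by the entry criteria while matching a listed example of a major deviation.

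Read mechanically, that would remove visits from someone who broke no rule. The peak rows use only visits kept in the population concerned (SAP Table 15, implementation note), so a participant vaccinated between doses 1 and 2 could be left with Day 8, before doses 2 and 3, as the per-protocol peak. With about 10 people per arm, one such case would show in the tables.

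Two further points looked untidy. The bullets nest differently in the two documents, which raised the question of which data are removed. The SAP's out-of-window rule also looks stricter than the protocol's.

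**Working it through.** **Reference figure.** The only sizing figure in the documents is the interval for 0 events in 10 people (Protocol 9.2, SAP 5). Its Clopper-Pearson upper limit is 1 − 0.025^(1/10) = 30.8%, which agrees with the stated 31%.

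**Days in dispute.** Doses fall on Days 1, 29 and 57 (SAP 4.4.5), that is, at offsets 0, 28 and 56.
- Span from 14 days before dose 1 to 14 days after dose 3: offsets −14 to 70, 85 days. All lie within 14 days of a dose.
- Within ±7 days of a dose: 3 × 15 = 45 days.
- Remaining, 8–14 days from the nearest dose: 85 − 45 = 40 days, made up of 7 before dose 1, 13 + 13 between doses and 7 after dose 3.
- With both intervals at 30 days: span 89 days, 89 − 45 = 44 outside ±7, of which 42 lie within 14 days.

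**Visits lost if the bullet were applied mechanically.** Serum visits are Days 8, 29, 36, 57, 64, 85 and 113; ALS (lymphocyte supernatant) visits are Days 8, 36 and 64 (SAP 3.3).

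| Timing of shot | Serum lost (of 7) | ALS lost (of 3) |
|---|---|---|
| 8–14 days before dose 1 | 7 | 3 |
| Days 9–21 | 6 | 2 |
| Days 37–49 | 4 | 1 |
| Days 65–71 | 2 | 0 |

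If one person drops out of an arm of 10 at a visit, the upper limit for 0 responders becomes 1 − 0.025^(1/9) = 33.6% instead of 30.8%.

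**What the texts require under each reading.**
1. *The ±7-day clause is an exception.* A shot 8–14 days away complies with the entry criteria. Protocol 5.5 makes noncompliance the test of a deviation, so this is not one. The vaccine line, which illustrates major deviations, does not reach it, and the visits stay.
2. *The ±7-day clause is an added restriction.* A licensed inactivated influenza vaccine 8–14 days away then breaches exclusion 14 or criterion 4. Eligibility and the per-protocol rule agree. DMID classifies the deviation (SAP 7.2), and the review in SAP 6.3.3 decides whether visits go. The clause still has work to do here, for any influenza or COVID-19 product that is neither a licensed inactivated nor a licensed live vaccine.

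**Which data go.** The closing sentence of SAP 6.3.3 limits removal to the affected visit and those after it. In Protocol 9.4.1 the top-level exclusions start from data, whereas the vaccine line starts from receipt of a product, as the incorrect-vaccination sub-item does. The difference in nesting is most likely a matter of layout.

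**The case for a change.** The strongest argument for a change is that the safeguards start from deviations. If the exception reading is right, a shot at 8–14 days need not reach the review at all, while a programmer working from the bullet could still flag it. If it does reach review, no criterion says how to decide. The case is also foreseeable: screening asks every participant about influenza and COVID-19 vaccines (Protocol 5.1), and non-study vaccines are recorded (SAP 4.4.7). One sentence would settle it, with no new data and no new analysis.

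Part of this stands. The intent of the ±7-day clause is not written down, and the omission of the adverb from the out-of-window rule is a real difference that SAP 15 does not mention. But a shot that never counts as a deviation is a shot whose visits are kept, which is the right result under that reading. Automatic loss of visits would require applying the bullet against both its own heading and the review sentence. Nor must the per-protocol set mirror eligibility: it may be stricter, so a rule that no permitted vaccine can lead to exclusion would be a preference rather than a correction. The out-of-window point is separate and lends no support here. Such visits are themselves deviations and go through the same blinded review.

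**Conclusion.** This is a gap in detail that the planned process fills sensibly, together with one unlisted wording difference. The plan can be followed as written.

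At most, a mechanical reading would take 2 to 7 of 7 post-baseline serum visits, and 0 to 3 of 3 ALS visits, from each person with such a shot, in the per-protocol tables only. Every one of those tables has a counterpart in the Full Immunogenicity Population (SAP 11.2 and 11.3) that would not change, and the Safety Population is untouched. The immunogenicity endpoints are secondary or exploratory, and SAP 6.8 plans no testing, so no error rate or decision rule depends on the classification. Table 9 and Listings 5 and 8 show exclusions with their reasons, so a reader could see any such case and compare the two populations.

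The conclusion assumes that the review before lock is carried out with the recorded non-study vaccinations in view. Two things cannot be checked from the documents: how many people had an influenza or COVID-19 vaccine in the 8–14 day band, since the 40 of 85 is a count of calendar days, and which vaccine windows applied to Cohort 1, which was enrolled under protocol v4.0 (SAP 4.3). Neither affects the Full Immunogenicity or Safety results. Nothing here says which vaccine window is right.

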## 6.4. Covariates and Subgroups

The protocol does not define any formal subgroup analyses, and the study is not adequately powered to perform subgroup analyses.

## 6.5. Missing Data

All attempts will be made to collect all data per protocol. As missing data are expected to be minimal, no imputation will be performed for missing values. Any data point that appears to be erroneous or inexplicable based on clinical judgment will be investigated as a possible outlier. If data points are identified as outliers, sensitivity analyses will be performed to examine the impact of including or excluding the outliers. Any substantive differences in these analyses will be reported.

All immunogenicity variables have a lower limit of quantification (LLOQ). Results that are <LLOQ will be imputed as the limit of detection (LOD) in calculations of summary statistics in tabular and graphical displays. The CRM197-specific IgG and IgM assays have a 3-fold titration series, so the imputed value will be  $LOD = 1/3 * LLOQ$ . The *C. jejuni* capsule-specific serum IgG and IgM and ALS IgG assays have a 2-fold titration series, so the imputed value will be  $LOD = 1/2 * LLOQ$ . Imputed values will be rounded to the nearest whole number for consistency with conversion of results from  $\log_{10}$  titer to titer. The number of results <LLOQ will be reported in tabular summaries.

Immune Response	LLOQ		
	Log 10 Titer	Titer	Imputed Titer when <LLOQ
C. Jejuni Capsule-specific IgG Serum Antibody	2.30	200	100
C. Jejuni Capsule-specific IgM Serum Antibody	2.30	200	100
CRM 197 -specific IgG Serum Antibody	3.00	1000	333
CRM 197 -specific IgM Serum Antibody	2.00	100	33
C. Jejuni Capsule-specific IgG ALS Antibody	0.70	5	3

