### 3.3. Study Definitions and Derived Variables

Unless otherwise specified, the baseline value will be defined as the last value obtained prior to the first vaccination. Vital signs assessed on Day 1 prior to study vaccination will be considered as baseline. Any medical condition that is present at the time that the participant is screened will be considered as baseline and will only be reported as an AE if symptoms related to the condition occur with greater frequency and/or severity after vaccination during the AE reporting period.

Change from baseline is defined as the additive change from baseline, i.e.,  $CHG_{ij} = y_{ij} - y_{i0}$  where  $y_{ij}$  is the measurement for participant  $i$  at time point  $j$  and  $y_{i0}$  is the measurement for participant  $i$  at baseline (prior to vaccination 1).

Fold-rise (FR) from baseline is defined as the multiplicative change from baseline, i.e.,  $FR_{ij} = \frac{y_{ij}}{y_{i0}}$  where  $y_{ij}$  is the response for participant  $i$  at time point  $j$  and  $y_{i0}$  is the response for participant  $i$  at baseline (pre-vaccination 1). Individual FR values will be reported to 1 decimal place.

The peak titer and peak fold-rise are defined as the maximum value for a participant at any time after the first vaccination.

A responder is defined as having  $\geq 4$ -fold increase relative to baseline, i.e.,  $FR_{ij} \geq 4$  for participant  $i$  at post-baseline time point  $j$ . For serum assays, participants are classified as responders or not at Days 8, 29, 36, 57, 64, 85, and 113; for the ALS assay, participants are classified as responders or not at Days 8, 36, and 64.

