Time Point	Statistic	1 µg CJCV2 (N=X)	1 µg CJCV2+ALFQ (N=X)	3 µg CJCV2 (N=X)	3 µg CJCV2+ALFQ (N=X)	10 µg CJCV2 (N=X)	10 µg CJCV2+ALFQ (N=X)
56 Days Post Vaccination 3 (Study Day 113)	Titer: Min, Max	x, x	x, x	x, x	x, x	x, x	x, x
	FR: GM (95% CI) b	x.xx (x.xx, x.xx)	x.xx (x.xx, x.xx)	x.xx (x.xx, x.xx)	x.xx (x.xx, x.xx)	x.xx (x.xx, x.xx)	x.xx (x.xx, x.xx)
	FR: Min, Max	x.x, x.x	x.x, x.x	x.x, x.x	x.x, x.x	x.x, x.x	x.x, x.x
	Responders c (95% CI) d	xx.x (xx.x, xx.x)	xx.x (xx.x, xx.x)	xx.x (xx.x, xx.x)	xx.x (xx.x, xx.x)	xx.x (xx.x, xx.x)	xx.x (xx.x, xx.x)
Post Vaccination Peak Titer	n	x	x	x	x	x	x
	Number <LLOQ a	x	x	x	x	x	x
	Titer: GM (95% CI) b	x.x (x.x, x.x)	x.x (x.x, x.x)	x.x (x.x, x.x)	x.x (x.x, x.x)	x.x (x.x, x.x)	x.x (x.x, x.x)
	Titer: Min, Max	x, x	x, x	x, x	x, x	x, x	x, x
	FR: GM (95% CI) b	x.xx (x.xx, x.xx)	x.xx (x.xx, x.xx)	x.xx (x.xx, x.xx)	x.xx (x.xx, x.xx)	x.xx (x.xx, x.xx)	x.xx (x.xx, x.xx)
	FR: Min, Max	x.x, x.x	x.x, x.x	x.x, x.x	x.x, x.x	x.x, x.x	x.x, x.x
	Responders c (95% CI) d	xx.x (xx.x, xx.x)	xx.x (xx.x, xx.x)	xx.x (xx.x, xx.x)	xx.x (xx.x, xx.x)	xx.x (xx.x, xx.x)	xx.x (xx.x, xx.x)
Notes: N = Number of participants in the Full Immunogenicity Population; n = Number of participants in the Full Immunogenicity Population with valid results at the given time point; GM = Geometric Mean; CI = Confidence Interval; Min = Minimum; Max = Maximum; FR = Fold-rise in antibody titer compared to pre-vaccination 1; LLOQ = Lower Limit of Quantification; LOD = Limit of Detection.							
a Number of participants in the Full Immunogenicity Population whose result was <LLOQ at the given time point; result is imputed as LOD in summary statistics.							
b 95% confidence interval based on Student's t distribution.							
c Percentage of participants with FR ≥ 4.							
d Exact 95% Clopper-Pearson confidence interval.							

Tables with similar format:

**Table 16:** *C. jejuni* Capsule-specific IgG Serum Antibody Results with 95% Confidence Intervals by Time Point and Treatment Group, PP Immunogenicity Population

**Table 17:** CRM197-specific IgG Serum Antibody Results with 95% Confidence Intervals by Time Point and Treatment Group, Full Immunogenicity Population

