## 16.2.6 Individual Immunogenicity Response Data

### Listing 8: Individual Immunogenicity Response Data

*[Implementation Note: The “Result (Log10 Titer)” column will show the results as reported by the lab; results below the limit of quantification will display “< LLOQ” where LLOQ will be replaced by the actual LLOQ for the assay. The “Result (Titer)” column will show the Log10 Titer result converted to Titer as specified in Section 4.5.2; results <LLOQ will be imputed as specified in Section 6.5. The “Actual Study Day” column will be the day relative to first vaccination where Study Day 1 is the day of first vaccination and Study Day -1 is the day prior to first vaccination. The “Analysis Time Point” column should use the same labels as the summary tables. The columns to indicate whether each value was included in the analysis will be “Yes” if the value is included, “Yes – Imputed Value” if the value was imputed because it was <LLOQ, or “No[x]” where [x] will be a footnote indicating the reason for exclusion. If the reason for exclusion is because the participant was excluded from the analysis population, only that reason needs to be included; otherwise, include all applicable reasons separated by commas. The footnotes are example reasons for exclusion; only include the reasons observed in the study. In the CSR, Participant ID should be USUBJID (not PATID) for purposes of de-identification. Sort by Treatment Group, Participant ID, Actual Study Day, and Assay. Note that the values in the table are meant to represent possible values expected for that column and are not necessarily associated with entries in other columns in the same row.]*

Treatment Group	Participant ID	Analysis Time Point	Actual Study Day	Assay	Result (Log 10 Titer)	Result (Titer)	Included in Full Immunogenicity Population?	Included in PP Immunogenicity Population?
1 µg CJC2	EHD.XXXXX	Pre-Vaccination 1 (Study Day 1)	X	C. jejuni Capsule-specific IgG Serum Antibody	X.XX	XX	Yes	Yes
1 µg CJC2+ALFQ		7 Days Post Vaccination 1 (Study Day 8)		CRM 197 -specific IgG Serum Antibody	< [LLOQ]		Yes – Imputed Value	Yes – Imputed Value
3 µg CJC2		Pre-Vaccination 1 (Study Day 29)		C. jejuni Capsule-specific IgG ALS			No [x]	No [x]
3 µg CJC2+ALFQ		7 Days Post Vaccination 2 (Study Day 36)		C. jejuni Capsule-specific IgM Serum Antibody				

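### SAP 6.5 rounds the imputed ALS titer from 2.5 up to 3, so a two-step ALS rise from below the LLOQ to 10 computes as 3.33-fold and is not counted as a response

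*SAP*

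**What the plan says.** SAP 6.5 (Missing Data) handles censored assay results by substitution: "Results that are <LLOQ will be imputed as the limit of detection (LOD) in calculations of summary statistics in tabular and graphical displays". The LOD is tied to each assay's dilution series. The two CRM197 assays use one third of the LLOQ. The capsule serum assays share a rule with ALS: "ALS IgG assays have a 2-fold titration series, so the imputed value will be" half the LLOQ. A rounding step follows: "Imputed values will be rounded to the nearest whole number for consistency with conversion of results" from the log10 scale. The table in that section gives LLOQ titers of 200, 200, 1000, 100 and 5 (capsule IgG, capsule IgM, CRM197 IgG, CRM197 IgM, ALS IgG) and imputed titers of 100, 100, 333, 33 and 3.

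SAP 3.3 defines fold-rise as the post-baseline response divided by the pre-vaccination 1 response, and a responder as a participant whose fold-rise is at least 4. It adds that "for the ALS assay, participants are classified as responders or not at Days 8, 36, and 64" and that "Individual FR values will be reported to 1 decimal place".

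The imputed titer carries through to the outputs. ALS Tables 19 and 20 follow the format of Table 15. Its footnote on results below the LLOQ says "result is imputed as LOD in summary statistics", and its responder row is the "Percentage of participants with FR ≥ 4". For the titer column of Listing 8, "results <LLOQ will be imputed as specified in Section 6.5". Nothing in the SAP exempts ALS, fold-rise or responder status from the rounded value.

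**The concern.** The LOD rule has a clear logic: a result below the LLOQ is placed one dilution step under it. On a 2-fold series, two steps up from there should then be exactly a 4-fold rise, which is the responder threshold. Rounding to a whole number preserves this when the LLOQ is in the hundreds. With an LLOQ of 5 the rounding shift is a large fraction of the value, and the imputed titer no longer sits one step below the LLOQ.

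At stake is the meaning of an ALS response. Participants below the LLOQ at baseline would face a stricter cutoff than participants at 5 or above in the same assay, and the reported ALS fold-rises and geometric means would not follow the half-LLOQ convention that the section sets out.

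**Working it through.** **Inputs.** LLOQ titers, LOD fractions and the rounding rule come from SAP 6.5. Fold-rise (FR = later titer / baseline titer) and the threshold FR ≥ 4 come from SAP 3.3.

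**1. Reproduce the SAP's imputed titers.**

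| Assay | LLOQ | LOD before rounding | SAP value | Change |
|---|---|---|---|---|
| Capsule IgG, serum | 200 | 200/2 = 100 | 100 | 0% |
| Capsule IgM, serum | 200 | 200/2 = 100 | 100 | 0% |
| CRM197 IgG, serum | 1000 | 1000/3 = 333.33 | 333 | -0.1% |
| CRM197 IgM, serum | 100 | 100/3 = 33.33 | 33 | -1.0% |
| Capsule IgG, ALS | 5 | 5/2 = 2.5 | 3 | +20% |

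All five tabulated values reproduce. Only ALS moves materially.

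**2. Effect on one fold-rise.** For a baseline below the LLOQ and a quantifiable later titer y, the SAP gives y/3 and the half-LLOQ convention gives y/2.5. The ratio is 2.5/3 = 0.83 whatever y is. If both results are below the LLOQ, FR is 1 either way.

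**3. Effect on responder class, ALS baseline below the LLOQ.**

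| Later titer | FR with 3 | FR with 2.5 | Class changes? |
|---|---|---|---|
| 5 | 1.67 | 2.0 | no |
| 10 | 3.33 | 4.0 | yes |
| 11 (off-grid) | 3.67 | 4.4 | yes |
| 12 (off-grid) | 4.0 | 4.8 | no |
| 20 | 6.67 | 8.0 | no |

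Rounding FR to one decimal first does not help: 3.3 and 3.7 are still below 4. On the 2-fold grid (5, 10, 20, ...) only 10 changes class, so a participant starting below the LLOQ must reach 20 to count.

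**4. The same two-step rise elsewhere.** ALS 5 to 20 is 20/5 = 4.0, a response. Capsule serum from below the LLOQ to 400 is 400/100 = 4.0, a response. ALS from below the LLOQ to 10 is also two steps, and it fails at 3.33.

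**5. Geometric summaries.** Let f be the share of participants going from below the LLOQ to quantifiable, minus any share going the other way. The ALS GMFR is multiplied by (2.5/3)^f. Let p be the share below the LLOQ at a visit. The ALS GMT at that visit is multiplied by 1.2^p. Neither f nor p is in the documents, so these are illustrations:

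- GMFR: 0.96 at f = 0.25, 0.91 at f = 0.5, 0.83 at f = 1.
- GMT: 1.10 at p = 0.5, 1.20 at p = 1.

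**6. What does not move.** The Spearman correlations in Tables 28 and 29 use ranks. Both 2.5 and 3 lie below the LLOQ of 5, so the ALS ranks are the same. The imputed value for capsule serum IgG, the secondary endpoint, is exactly 100 with or without rounding.

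**The case against.** The strongest reply is that there is no mistake in the table. SAP 6.5 states the rounding step, gives a reason for it and prints the resulting 3, and the SAP then computes with exactly that value. This stands. A reader might infer an arithmetic slip, but the documents do not support that. The problem is what the rule produces when applied to an LLOQ of 5.

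A second reply is that 2.5 is no truer than 3. The result is censored somewhere below 5, and half the LLOQ is itself a convention. This also stands, so it would go too far to say that the ALS GMFR is biased against a known truth. What can be said is that the SAP adopts half the LLOQ, which makes a two-step rise 4-fold, and then departs from it in one assay only.

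A third reply concerns importance. ALS is exploratory (SAP 3.2), no testing is planned (SAP 6.8), counts below the LLOQ are tabulated, and Listing 8 flags imputed values, so a reader could redo the calculation. This limits the severity. It does not remove the inconsistency, because the reported responder percentages would still apply two cutoffs within one assay.

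**Conclusion.** The rule is wrong as written, with minor severity. For participants below the ALS LLOQ at baseline, the rounded denominator makes the responder threshold 12 in titer units (4 × 3) instead of 10 (4 × 2.5), and each fold-rise to a quantifiable value is 0.83 times its half-LLOQ value. Class changes only at a later titer of 10, or also 11 if titers off the 2-fold grid occur. With 10 participants per group (SAP 5), each one reclassified moves a group's responder rate by 10 percentage points.

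The 4.0 for a rise to 10 uses the tabulated whole-number LLOQ of 5. If the LOD were taken from 10^0.70 = 5.012, it would be 2.506, which also rounds to 3, and the same rise would be 3.99.

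A reader might go on to infer a particular drop in the ALS responder rate, or an effect on the trial's main immunogenicity results. The documents support neither. They give no distribution of ALS titers and no share below the LLOQ, so the number affected cannot be known. The effect is limited to the reported ALS responder rates, GMFR and GMT.

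**What to change.** In SAP 6.5, state that the ALS imputed value used in fold-rise, responder and GMT calculations is the unrounded 2.5, and that rounding applies only to display. Change the ALS cell of the table to match, and add a short footnote to Tables 19 and 20 and Listing 8 so that a displayed 3 is not taken as the denominator. No other assay's imputed value needs to change.

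The cost is one sentence, one table cell, the footnotes and one line of derivation code, with no new data. It is best done before database lock. After lock, the SAP's preface allows a deviation to be described and justified in the CSR.
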